#### **4.2 Dose Modification:**

Dose will be reduced from 1.8 mg/kg to 1.2 mg/kg or from 1.2 mg/kg to 1 mg/kg or from 1 mg/kg to stop treatment if:

1. Neutropenia grade 3-4 unresponsive to G-CSF or grade 4 thrombocytopenia are observed.
2. Peripheral neuropathy, new or worsening grade 2 or 3. Withhold treatment until improvement or return to grade 1 or baseline; then resume with a dose reduction.

Dose will be reduced to 1 mg/kg if:

1. Creatinine clearance < 30 cc/min as defined by MDRD method from NKDEP.  
<http://nkdep.nih.gov/lab-evaluation/qfr/estimating.shtml>
2. Hepatic impairment defined as bilirubin > 2 mg/dL.

If the patient develops grade 3-4 neutropenia unresponsive to G-CSF: Hold until resolution to grade </= 1 and restart at lower dose.

#### **4.3 Treatment will be discontinued if:**

1. If the dose that was administered was 1 mg/kg and the patient develops grade 4 hematological toxicity as described above.
2. If the patient develops both foscarnet and ganciclovir-resistant CMV viremia or histologic CMV end-organ disease.
3. If an anaphylactic reaction is observed.
4. If peripheral neuropathy, grade 4 is observed.
5. If progressive multifocal leukoencephalopathy (PML) is confirmed. Treatment must be withheld until PML is confirmed.
6. If the patient develops Stevens-Johnson syndrome.

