## 4.0 Treatment Plan

### 4.1 Treatment Initiation:

Brentuximab will be given as an IV infusion over 30 minutes every 3 weeks for a total of 6 cycles. starting between days 35 and 60 post allogeneic SCT.

Brentuximab dose will be based on actual body weight starting with an initial dose of 1.2 mg/kg for the first 2 cycles and then the dose will be increased to 1.8 mg/kg after the second cycle for all subsequent cycles. Brentuximab dose will be based on actual body weight except for patients weighing more than 100 kg, then dose will be calculated based on 100 kg.

Patients must meet the following criteria to start any cycle of brentuximab:

1. Absolute neutrophil count > 1,000/mm^3 not requiring daily growth factor support on the day of the brentuximab infusion.
2. Platelet count greater than 50,000/mm^3 independent of platelet transfusions or thrombopoietin factor for at least 5 days.
3. No clinical evidence of life-threatening infection.

4. No active bleeding.
5. No uncontrolled acute GVHD (steroid refractory).
6. No CMV re-activation that is dual-refractory to foscarnet and ganciclovir/ No active CMV disease.
7. Creatinine < 1.5 mg/dL or creatinine clearance greater than or equal to 40 cc/min as defined by MDRD method from National Kidney Disease Education Program (NKDEP)
8. Serum bilirubin < 1.5 mg/dL
9. SGPT < 200 IU/L unless related to patient's malignancy

Vital sign monitoring, observation, and treatment of hypersensitivity reactions during and after infusion will be performed per standard of care.

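### At 1 mg/kg, sections 4.2 and 4.3 conflict on whether grade 3 neutropenia unresponsive to G-CSF ends treatment

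*Combined protocol and SAP*

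**What the plan says.** Section 4.1 plans brentuximab "every 3 weeks for a total of 6 cycles", at 1.2 mg/kg for two cycles and 1.8 mg/kg after that. Section 4.2 sets a ladder for toxicity: 1.8 to 1.2 mg/kg, 1.2 to 1 mg/kg, and as the last step "from 1 mg/kg to stop treatment if" one of two listed triggers occurs. The first trigger is haematological: "Neutropenia grade 3-4 unresponsive to G-CSF or grade 4 thrombocytopenia are observed". The second is new or worsening peripheral neuropathy of grade 2 or 3, with the instruction "Withhold treatment until improvement or return to grade 1 or baseline; then resume with a dose reduction".

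After the ladder and a separate renal and hepatic rule, 4.2 closes with a free-standing line on grade 3-4 neutropenia unresponsive to G-CSF: "Hold until resolution to grade </= 1 and restart at lower dose".

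Section 4.3 lists the reasons for discontinuing. Item 1 is "If the dose that was administered was 1 mg/kg and the patient develops grade 4 hematological toxicity as described above". Item 4 is "If peripheral neuropathy, grade 4 is observed".

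**The concern.** Three sentences bear on one patient: someone at 1 mg/kg with grade 3 neutropenia unresponsive to G-CSF. One stops treatment. One holds it and then restarts at a dose that the protocol does not contain. One restates the discontinuation rule for this dose and leaves grade 3 out.

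These are patient-level safety rules at the bottom of the dose range, applied soon after an allogeneic transplant. While the count is low there is no practical difficulty, because nobody would be dosed. The difficulty comes on recovery, when the clinician must decide whether treatment is over or may resume. Two clinicians could read the same pages and decide differently.

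**Working it through.** No arithmetic applies, since the point depends on no rate, sample size or error level. The check is to set the rules for a patient at 1 mg/kg side by side.

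| Event at 1 mg/kg | 4.2 ladder | Other instruction in 4.2 | 4.3 | Settled? |
|---|---|---|---|---|
| Grade 3 neutropenia, unresponsive to G-CSF | Stop | Hold, then restart lower (closing line) | Not listed | No |
| Grade 4 neutropenia, unresponsive to G-CSF | Stop | Hold, then restart lower (closing line) | Stop (item 1) | Yes: two explicit stop rules |
| Grade 4 thrombocytopenia | Stop | None | Stop (item 1) | Yes |
| New or worsening grade 2-3 neuropathy | Stop | Withhold, then resume reduced (inside the ladder's own item 2) | Not listed; item 4 concerns grade 4 | Yes by the ladder lead-in, though the wording could be clearer |

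Only the first row has a stop rule in one place, an incompatible instruction in another, and no entry in 4.3.

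**Is there a dose below 1 mg/kg?** None appears in the protocol. The closing line of 4.2 therefore cannot be carried out at this level, and it has no exception for it.

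**Does 4.3 item 1 import the 4.2 triggers?** It refers back to them, so it reads as a restatement of the ladder's last step. But it names grade 4, whereas the 4.2 trigger for neutropenia is grade 3 or 4. The grade threshold differs between the two sections.

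**Does another section settle the matter?**
- Section 4.1 item 1 requires an absolute neutrophil count above 1,000/mm³, "not requiring daily growth factor support on the day of the brentuximab infusion". That prevents dosing while the count is low. It does not say whether a patient who again meets the criterion may continue.
- Section 4.4, on events that do not lead to reduction or stopping, covers new-onset GVHD and infusion reactions. It is silent on neutropenia.
- Off-study criterion 6.2 covers a patient who cannot tolerate treatment. It gives no grade and no dose.

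**Can a patient be at 1 mg/kg?** Yes, by three routes: the ladder, the renal and hepatic rule in 4.2, and section 8.1, which makes 1 mg/kg the starting dose for all patients if toxicity above grade 3 is seen at 1.2 mg/kg. Section 2.5 reports grade 3 or higher neutropenia in 24% of patients treated at 1.8 mg/kg after relapse following an allogeneic transplant. That shows the event type is not rare. It is not a rate at 1 mg/kg, nor a rate of neutropenia unresponsive to G-CSF, so no expected count can be derived from it.

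**The case against.** The best defence is that the ladder already answers the question. It says to stop at 1 mg/kg, no passage authorises a repeat dose at 1 mg/kg, and the closing line cannot send anyone to a dose that does not exist. Stopping is then the only defined action. This is the natural reading, and it limits the weight of the point. It does not remove it: the closing line stands outside the ladder's list, is written without exception, and tells the clinician to restart after recovery.

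A reader might go further in three ways that the documents do not support.

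- *That 4.3 permits treatment to continue after grade 3 neutropenia at 1 mg/kg.* Section 4.3 is not worded as an exclusive list. It omits the grade 3 stop and does not forbid it.
- *That neuropathy is in the same conflict.* The instruction to resume at a reduced dose belongs to item 2 under the ladder's lead-in, which already says to stop at 1 mg/kg. It can be read as applying to the two steps where a reduction exists. Item 4 of 4.3 deals with grade 4, above the ladder's grades 2 and 3, and does not contradict it.
- *That grade 4 neutropenia is also unresolved.* The closing line covers it, but the ladder and 4.3 item 1 both say stop.

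**Conclusion.** The inconsistency is real and narrow. It concerns grade 3 neutropenia unresponsive to G-CSF at 1 mg/kg, and in practice the patient who has recovered from it. Stopping is the natural reading, but the text does not secure it.

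The documents give no basis for the number of patients affected. It is likely to be small, because a patient must first be at the lowest dose and then have this specific event. A reader might infer that the trial's safety conclusions are at risk. They are not: the graft-failure endpoint and its stopping limit in 8.2, the planned 20 patients, and the trial-level triggers in 8.1 and 8.3 are all defined independently of these lines. The point is worth correcting because it is a clash between stated safety rules and not merely missing detail, but it is of low priority.

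This conclusion assumes that the 4.2 ladder expresses the intended rule. If grade 4 alone was meant to end treatment at 1 mg/kg, the ladder is the sentence to change, and the protocol would then have to state the dose at which a patient recovering from grade 3 resumes.

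**What to change.** 1. In 4.3 item 1, replace the grade 4 wording with the 4.2 haematological triggers: at 1 mg/kg, discontinue for neutropenia of grade 3 or 4 unresponsive to G-CSF, or for thrombocytopenia of grade 4.
2. In the closing line of 4.2, limit the restart to patients at 1.8 or 1.2 mg/kg, and add that a patient at 1 mg/kg discontinues.
3. Optionally, add the same clause to the neuropathy item in 4.2. The lead-in already implies it, so this is only a clarification.

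The cost is a wording amendment to 4.2 and 4.3. Visits, sample size and analysis stay as they are.

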#### **4.4 Treatment will not be dose reduced or stopped for:**

1. New onset GVHD.
2. An infusion reaction, in which case the infusion will be interrupted and appropriate medical intervention will be administered. Pre-medicate subsequent infusions with acetaminophen, an antihistamine, and/or a corticosteroid.

## **5.0 Evaluation During Treatment**

#### **5.1 Prior to the first cycle (within 5 days prior to receiving first dose of brentuximab):**

1. Physical exam including GvHD assessment.
2. CBC with diff and platelets, chemistries.
3. Correlative studies: blood sample for immunophenotyping studies prior to 1st dose, and 1, 3,

and 5 days after first brentuximab dose.

4. Chimerism studies in peripheral blood.

**5.2 At each subsequent cycle (within 5 days prior to receiving first dose of brentuximab in each cycle):**

1. Physical exam including toxicity and GVHD assessment.
2. CBC with diff and platelets, chemistries.
3. Correlative studies: blood sample prior to the brentuximab dose.

**5.3** If patient has a biopsy (skin, GI or liver) at any time for GVHD diagnosis, a blood sample (10 mL) will be taken at that time for correlative studies.

**5.4** To be performed at approximately 1, 3, 6 and 12 months post-transplant.  
These evaluations follow our standard practice and are done to monitor engraftment and disease status. If clinically indicated these studies may be done at other time points which can replace the nearest planned timepoint.

1. Chimerism studies from peripheral blood performed on separated T-cells and myeloid cells.
2. At each visit, physical examination and adverse event documentation including GvHD assessment.
3. Disease specific assessment with bone marrow aspirate with cytogenetics, serum immunoglobulins in peripheral blood and CT for lymphoma staging as indicated.

**5.5 Correlative Studies to be performed by Dr. [name] in her laboratory (no cost to the patients):**

**5.5.1** T cell immunophenotyping to define:

- a. "naïve" (CD45RO-CCR7+) T cells.
- b. "effector memory" (CD45RO+CCR7-) T cells.
- c. "central memory" (CD45RO+CCR7+) T cells.
- d. "terminally differentiated effector memory" (CD45RO-CCR7-) T cells.
- e. "regulatory" T cells (CD4+CD25+CD127loFoxp3+).

**5.5.2** Functional T cell studies to assess impact of brentuximab on T cell function and recovery including regulatory T cell subsets; will co-stain with CD30. CD30 is also expressed on NK cells and can assess impact of brentuximab on NK cells.

**5.5.3** Functional studies of antigen-specific T cell responses to pathogens (CMV and EBV), and if impact on pathogen-specific T cell recovery.

**5.5.4** Determine impact of brentuximab on diversity of reconstituting T cell repertoire by flow cytometric analysis.

**5.6 To be done with collaboration with pathology department** - Assess tissue biopsies from GVHD sites for CD30 expression. Tissue biopsies with matched disease and site specific GvHD will be collected and used for controls to evaluate CD30 expression in brentuximab treatment patients. (if done for CD30+CD8+ or CD30+CD4+ T cell infiltration)

## 6.0 Study Criteria

### Off Study Criteria:

- 6.1 Patient withdraws consent.
- 6.2 Patient can not tolerate treatment.
- 6.3 Unexpected pattern of toxicity.
- 6.4 Presence of both steroid and 2nd line treatment refractory GvHD while on treatment with brentuximab.
- 6.5 Presence of dual-refractory CMV reactivation to foscarnet and ganciclovir or CMV end-organ disease while on treatment with brentuximab.

- 6.6 Patient's inability of unwillingness to have follow-up visits and/or laboratory tests required by this protocol.
- 6.7 One year after treatment completion.

**Steroid refractory GVHD** is defined as: absence of any response 7 days after the initiation of corticosteroids for skin GVHD or 10-14 days after its initiation for GI and liver GVHD. Patients who are steroid refractory are not eligible to be enrolled on protocol, however if a patient develops GVHD while on protocol, brentuximab will not be held.

**Secondary graft failure** is defined as a sustained declined of ANC  $<0.5 \times 10^9/L$  for 3 consecutive days after initial documented engraftment with no evidence of disease progression and is not associated with concomitant medication that is known to cause cytopenias.

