## 8.0 Statistical Considerations

Study Design

- 8.1 This is a phase II study in which brentuximab will be initiated after transplant (approximately day 35-60) post engraftment and restaging at day 30 (+10 days) and continued every 21 days for 6 cycles. Dose initiation will be at 1.2 mg/kg for 2 cycles and escalated to 1.8 mg/kg on subsequent 4 cycles. If greater than grade 3 toxicity seen at 1.2 mg/kg dose level then dose will be decreased to 1 mg/kg for all patients at initiation with subsequent cycles at 1.2 mg/kg dose. We will allow intrapatient dose modification based on toxicity.

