#### **8.3 Determination of hematologic toxicity and CMV disease**

The most common grade  $\geq 3$  side effects on brentuximab after allogeneic transplant(7) are neutropenia (24%), and thrombocytopenia (20%) which were reversible. CMV was detected in 5 patients and was clinically significant in 1 patient.

Brentuximab will be discontinued if patient develops dual foscarnet and ganciclovir-resistant CMV viremia or histologic CMV end-organ disease. In addition, the study drug will be reduced in all future patients if at any time there is >25% grade IV neutropenia rate or >10% CMV disease rate attributable to treatment observed within Day 45- Day 180.

These rates will be monitored in a continuous fashion.

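### Toxicity, refractory GVHD and CMV events are listed as reasons to leave the study and no follow-up after exit is stated, so graft failures inside the 6-month safety window may go uncounted

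*Combined protocol and SAP*

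**What the plan says.** Section 6.0 has one list, headed as off-study criteria. It holds consent withdrawal (6.1), intolerance (6.2, "Patient can not tolerate treatment"), unexpected toxicity (6.3), GVHD refractory to steroids and second-line treatment (6.4), CMV events (6.5, "Presence of dual-refractory CMV reactivation to foscarnet and ganciclovir or CMV end-organ disease while on treatment with brentuximab"), inability or unwillingness to attend follow-up (6.6) and the planned end (6.7, "One year after treatment completion").

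Section 4.3 is a separate list of reasons to stop the drug. It includes nearly the same CMV event: "If the patient develops both foscarnet and ganciclovir-resistant CMV viremia or histologic CMV end-organ disease". Section 8.3 also treats that event as stopping the drug: "Brentuximab will be discontinued if patient develops dual foscarnet and ganciclovir-resistant CMV viremia or histologic CMV end-organ disease".

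Section 8.2 defines safety as at most two secondary graft failures within 6 months of Day 0 and closes accrual if more than two are observed. Dosing starts between Day 35 and Day 60 (section 4.1) and is "continued every 21 days for 6 cycles" (section 8.1). Section 5.4 sets evaluations at about 1, 3, 6 and 12 months after transplant, including "At each visit, physical examination and adverse event documentation including GvHD assessment".

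**The concern.** The protocol has both ideas, off treatment and off study, but does not keep them apart. The CMV event stops the drug in 4.3 and 8.3 and ends study participation in 6.5. For events 6.2 to 6.5 no section says that follow-up continues, whether the patient stays in the graft failure denominator, or how PFS and OS are handled.

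Secondary graft failure is the primary objective, and its count triggers the study's stopping rule. If a patient leaves for toxicity, GVHD or CMV and then loses the graft before month 6, the failure may not reach the count. That error has one direction for the raw count: it can only make the stopping rule harder to reach.

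**Working it through.** **The plan's own figure.** Section 8.2 gives a 95% interval of 0-14.6% for a 5% incidence in 20 patients. The normal approximation reproduces it: 0.05 ± 1.96 × √(0.05 × 0.95/20) = 0.05 ± 0.0955, cut at zero. Nothing is wrong with that arithmetic, but it assumes that all 20 patients are ascertained.

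**Timing.** Six doses 21 days apart put the last undelayed dose 5 × 21 = 105 days after the first: Day 140 for a Day 35 start and Day 165 for a Day 60 start. Taking 6 months as 183 days, the window still open at exit is:

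| Exit after | Day 35 start | Day 60 start |
|---|---|---|
| dose 1 | 148 days | 123 days |
| dose 3 | 183 − 77 = 106 days | 183 − 102 = 81 days |
| dose 6 | 183 − 140 = 43 days | 183 − 165 = 18 days |

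Every exit during undelayed dosing therefore falls inside the window.

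**Effect on the stopping rule.** The documents give no exit rate and no fraction of later failures that would still be found. Assumed: 20 patients, 4 leavers, all free of failure at exit, constant hazard from first dose to Day 183, no excess risk in leavers. For true rate p and start day s, a leaver's risk after exit is

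r = 1 − (1 − p)^(days left / (183 − s)).

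For p = 10% and exit after dose 3, r = 1 − 0.9^(81/123) = 0.0670 (Day 60 start) to 1 − 0.9^(106/148) = 0.0727 (Day 35 start). With capture fraction c, the count is Bin(16, p) + Bin(4, r × c). The chance that it exceeds two is:

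| True rate | Full capture | Half | None |
|---|---|---|---|
| 5% (planning value in 8.2) | 0.064-0.066 | 0.053-0.054 | 0.043 |
| 10% (standard rate in 8.2) | 0.286-0.292 | 0.248-0.251 | 0.211 |
| 20% (assumed) | 0.753-0.760 | 0.703-0.707 | 0.648 |

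Ranges run from a Day 60 to a Day 35 start. As a check on the last column, with no capture only the 16 stayers count; at 10%, 1 − 0.9^16 − 16(0.1)(0.9^15) − 120(0.01)(0.9^14) = 0.211.

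**Sensitivity at 10%.** With exit after dose 6, full capture gives 0.228-0.244 against 0.211, so late exits matter little. With exit after dose 3, two leavers give 0.304-0.308 (full) against 0.266 (none), and six give 0.267-0.277 against 0.158.

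**Effect on incidence.** In the 10% case with 4 leavers after dose 3, the expected number of failures under full follow-up is 16 × 0.10 + 4 × (0.0670 to 0.0727) = 1.87-1.89, or 9.3-9.5% of 20. With none captured, keeping leavers as non-failures gives 1.6/20 = 8.0%. Dropping them gives 1.6/16 = 10.0%. The direction depends on the denominator, which is not stated.

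**Follow-up for PFS and OS.** A patient who completes six undelayed doses is followed under 6.7 to about Day 140 + 365 = 505 or Day 165 + 365 = 530. If follow-up ended at exit after dose 3, 505 − 77 = 530 − 102 = 428 days would be lost.

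**The case against.** The strongest reply is that this is a mislabelled off-treatment list. Criteria 6.4 and 6.5 apply only to events on brentuximab, 4.3 and 8.3 treat the CMV event as stopping the drug, and 6.6 covers failed follow-up separately. That is a plausible account of what was meant. But 6.6 and 6.7 in the same list can only be ends of participation, and nothing tells staff to read 6.2 to 6.5 differently.

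The second reply is that safeguards exist. The 5.4 visits run from transplant, are standard practice and are meant to monitor engraftment; the 6-month visit falls at the end of the window. Section 8.3 continuously monitors grade IV neutropenia and the "CMV disease rate attributable to treatment observed within Day 45- Day 180". (The attribution clause there may qualify only the CMV rate.) This stands in part, so zero capture is a worst case. It does not close the gap. Section 5.4 lists no blood count, and sections 5.1 and 5.2 schedule counts only before cycles, whereas the endpoint needs an ANC below 0.5 × 10^9/L on three days running. Neither provision is stated to continue after a patient goes off study.

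Third, the size is modest. In the 10% case with 4 leavers after dose 3, the expected loss is 4 × 0.0670 to 4 × 0.0727, about 0.27-0.29 of one failure. Since 10% is the standard-of-care figure, less stopping there is not in itself lost protection. That is fair; the 20% row shows the cost where the rule is needed, and that rate is assumed.

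**Conclusion.** The point holds as a gap in the stated rules. Followed as written, section 6.0 ends participation inside the 6-month graft failure window for the patients with toxicity, refractory GVHD or CMV events, and no follow-up is stated for them. With 4 of 20 leaving after dose 3, no capture lowers the chance of reaching the stopping rule by 0.02 at a true rate of 5%, 0.07-0.08 at 10% and 0.10-0.11 at 20%. These figures rest on an assumed exit share, exit time, constant hazard and capture fraction.

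Three stronger readings are not supported. A reader might infer that failures will be missed; the wording of 6.4 and 6.5 and the transplant-timed visits make this possible, not certain. A reader might infer that the drug must look safer; that is true of the raw count but not of an incidence that drops leavers from the denominator. And a reader might infer that PFS and OS are censored at these exits. Section 8.5 does not say so. It gives no rule at all, and if censoring at exit were applied it would probably be informative, which Kaplan-Meier estimation does not allow for.

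**What to change.** In section 6.0, state that when a patient stops brentuximab for a 6.2 to 6.5 event, outcome follow-up continues unless the patient withdraws consent to it or is unable or unwilling to be followed. In section 8:

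- keep every patient who receives at least one dose in the graft failure count and denominator;
- collect blood counts from routine post-transplant care through 6 months after Day 0;
- follow for relapse and survival to the planned end of follow-up, without censoring PFS or OS at these events;
- state how treatment completion in 6.7 is dated for patients who stop early.

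Sections 4.3, 6.5 and 8.3 must be reconciled on whether the CMV event ends brentuximab only or study participation. No clinical rule is proposed here, and outcome follow-up should continue however that is settled.

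The cost is wording plus slightly more data collection after treatment stops, since the 5.4 evaluations are already standard practice. One limit remains: routine counts may not always cover three consecutive days, so some failures could still go unconfirmed.

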### 2.0 Background

#### 2.1 Allogeneic hematopoietic stem cell transplants for Hodgkin lymphoma:

Hodgkin's lymphoma (HL) is primarily treated with conventional chemotherapy to which it is highly responsive(1). After relapse the standard of care is an autologous stem cell transplant (SCT) (2). The results of auto SCT are variable with recurrence of HL ensuing in 50% of patients after autologous SCT(3). Prognosis of patients who relapse following an auto SCT is generally poor, although allogeneic SCT can induce long-term remissions through a graft-vs.-lymphoma (GVL) effect. The use of myeloablative regimens for allogeneic SCT results in prohibitively high treatment related mortality (TRM), upward of 22% in the first 100 days(4). Reduced intensity conditioning (RIC) treatments have been shown to significantly reduce TRM, although relapse remains a significant problem. Anderlini and colleagues at our institution (5) have demonstrated decreased TRM using fludarabine/melphalan as conditioning with rates of TRM of 7% at day 100 and 15% at 2 years. Their data reveals an overall survival (OS) rate of 64% and progression free survival (PFS) of 32% at 2 years, with a 2-year rate of disease progression or relapse at 55%. In an EBMT analysis of 250 patients who received a reduced intensity allo SCT for found that chemorefractory disease was associated with PFS and OS of 8% and 25% respectively at 2 years. Patients in CR at time of transplant PFS had a 3-year PFS of 42%(6). Sureda et al.(3) reported on RIC allo SCT using fludarabine and melphalan and observed a TRM of 8% at 100 days and 15% at 1 year. The estimated PFS for the entire allografted population was 24% at 4 years and patients allografted in CR had PFS of 50% at 4 years. Alvarez et al.(8) found that patients allografted with chemosensitive disease (including CR patients) at time of transplantation had a PFS at 2 years of

55%  $\pm$  16%. These studies illuminate that although patients in CR and with chemosensitive disease have better outcomes, disease progression is still in the range of 50% 2-4 years post transplant. Reduced intensity allogeneic transplant can lead to long term disease free survival, however relapse after allo SCT has very poor outcomes with less than 50% of patients surviving past 3 years(7). Beyond allogeneic transplant there are limited effective therapeutic options.

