## **2.6 CD30 expression and Graft versus Host Disease:**

CD30 expression on CD8+ T cells may be a potential biomarker for acute GVHD.(20) Chen and colleagues recently published data analyzing CD30 expression on peripheral blood T-cell subsets and soluble CD30 levels in 26 patients at the time of onset of acute GVHD (aGVHD) treatment and then compared them to transplant patients without aGVHD.(22) Analysis by flow cytometry showed that patients with aGVHD had a greater percentage of CD30 expressing CD8+ T cells with the difference especially pronounced in the central memory subset (CD30+CD8+ CD45RO+ CD62L+). Levels of central memory CD30+CD8+ CD45RO+ CD62L+ cells were 6 times higher among patients with acute GVHD than among those without aGVHD. There were similar levels of CD30 expression in naive T cells, CD4+

T cells, and regulatory (CD4+CD127lowCD25+) T cells.1(10)

Plasma levels of soluble CD30 were significantly greater in patients with GVHD and immunohistochemical analysis of affected intestinal tissue showed many CD30+ infiltrating lymphocytes present. These results suggest that CD30 expression on CD8+T-cell subsets or plasma levels of soluble CD30 may be a potential biomarker for aGVHD.

In this study we will evaluate the safety of brentuximab early after allogeneic stem cell transplant and haploidentical allogeneic transplant and observe if there is a decrease in the risk of relapse.

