#### **8.5 Determination of the response and complete response rates in patients with measurable disease after day +30 restaging and progression free and overall survival of this regimen**

Kaplan-Meier (1958) survival curves will be used to estimate overall survival and progression-free survival. Cox proportional hazards regression analysis may be used to model the association between overall survival and progression-free survival and disease and demographic covariates of interest.

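### Follow-up ends one year after an undefined treatment completion, short of the 2-year rates in section 2.1, and patients taken off study early have no described follow-up

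*Combined protocol and SAP*

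**What the plan says.** Section 4.1 gives brentuximab "every 3 weeks for a total of 6 cycles", "starting between days 35 and 60 post allogeneic SCT". Section 6.0, criterion 6.7, takes a patient off study "One year after treatment completion". It does not say whether completion means the last dose, the end of the sixth cycle, or whatever point an early stopper reached.

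Criteria 6.2 to 6.5 also take patients off study: for intolerance of treatment, an unexpected toxicity pattern, GVHD refractory to steroids and second-line treatment, and dual-refractory CMV reactivation or CMV end-organ disease. No follow-up after these exits is described. Section 4.3 lists reasons for stopping the drug separately and does not say that those patients leave the study.

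Section 5.4 sets the disease assessments: "To be performed at approximately 1, 3, 6 and 12 months post-transplant". It adds: "If clinically indicated these studies may be done at other time points which can replace the nearest planned timepoint".

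Section 2.1 describes the course after allogeneic transplant for Hodgkin lymphoma as one where "disease progression is still in the range of 50% 2-4 years post transplant". For the institution's own series it gives 2-year PFS of 32% and 2-year progression or relapse of 55%. Section 2.6 says that the study will "observe if there is a decrease in the risk of relapse". Objectives 1.2.2 and 1.2.7 cover relapse, PFS and OS without a time point or comparator. Section 8.5 says only that "Kaplan-Meier (1958) survival curves will be used to estimate overall survival and progression-free survival", possibly with Cox models, and gives no landmark time or censoring rule.

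**The concern.** A single-arm study can see a fall in relapse only against outside rates, and the Hodgkin relapse and PFS rates in section 2.1 are all at 2 to 4 years. If planned follow-up stops earlier, an estimate from this trial set beside those rates will look favourable because it is read sooner, whether or not the drug works.

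Two further features affect the curves in section 8.5. The clock in 6.7 starts from treatment completion, so the length of follow-up may vary with the length of treatment. And 6.2 to 6.5 can remove patients early for reasons that plausibly bear on prognosis, OS in particular. Kaplan-Meier treats censoring as unrelated to outcome, and exits of this kind put that assumption at risk.

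**Working it through.** The plan states no follow-up length, landmark or event count for relapse, PFS or OS, so there is no figure on this point to reproduce. Its one precision figure, 0-14.6% for a 5% graft failure rate in 20 patients (section 8.2), is the Wald interval 0.05 ± 1.96 × √(0.05 × 0.95/20), truncated at zero. It is not an input here.

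**1. Length of follow-up.** Inputs: start on Day 35 to 60 and six 21-day cycles (section 4.1); one year (6.7). Assumptions: no dose delays; 30.44 days per month.

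| Anchor for completion | Anchor day | Off study (+365) | Months |
|---|---|---|---|
| Dose 6 (start + 105) | 140-165 | 505-530 | 16.6-17.4 |
| End of cycle 6 (start + 126) | 161-186 | 526-551 | 17.3-18.1 |
| Dose 1 only, if that counts as completion | 35-60 | 400-425 | 13.1-14.0 |

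Six-cycle patients stop 24 − 18.1 = 5.9 to 24 − 16.6 = 7.4 months short of 2 years. One-dose patients stop about 10 to 11 months short. For the same start day, a one-dose patient leaves 105 days before a six-dose patient, both counted from the last dose. The last scheduled disease assessment is at 12 months, so for six-cycle patients the final 4.6 to 6.1 months on study have none planned.

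**2. What an ineffective drug would show.** Take the section 2.1 institutional rates at 24 months and let S(t) = S(24)^((t/24)^k). The shape k is an assumption: k = 1 is constant hazard, k = 0.5 is front-loaded.

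- PFS at 12 months, k = 1: 0.32^0.5 = 0.566, about 57%.
- PFS at 12 months, k = 0.5: 0.32^0.707 = 0.447, about 45%.
- PFS at 17.4 months, k = 1: 0.32^0.725 = 0.438, about 44%.
- Relapse at 12 months, k = 1: 1 − 0.45^0.5 = 0.329, about 33%. For k = 0.5: 0.431, about 43%.

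Read against 32% at 2 years, the 12-month PFS is higher by 57 − 32 = 25 points or 45 − 32 = 13 points from timing alone.

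**3. Relapses that fall outside the schedule.** On the same model, the share of 2-year relapses after month 12 is (0.55 − 0.431)/0.55 = 22% for k = 0.5 and (0.55 − 0.329)/0.55 = 40% for k = 1. After 18.1 months the shares are 9% and 18%.

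**4. Early off-study exits.** The documents give no rate for exits under 6.2 to 6.5, so the number is an assumption. Let m of 20 patients leave before 12 months, with PFS of 57% in the rest. The all-patient value lies between 0.57 × (20 − m)/20 and [0.57 × (20 − m) + m]/20.

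| m | Lower bound | Upper bound |
|---|---|---|
| 2 | 51% | 61% |
| 4 | 46% | 66% |
| 6 | 40% | 70% |

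For scale, the 95% half-width with 20 patients and no censoring is 1.96 × √(p(1 − p)/20): 20 points at p = 0.32 and 22 points at p = 0.57.

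**The case against.** The strongest reply is that the plan promises no 2-year result. The 2-to-4-year figures are background, the objectives name no time point, and section 8.5 plans no historical comparison. This stands: a reader might infer that the objectives require a 2-to-4-year estimate, and they do not. A 12-month estimate remains obtainable. But section 2.6 sets out to look for a decrease in relapse, and the Hodgkin rates offered for judging one are at times that the planned follow-up does not reach.

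A reader might also infer that late estimates come only from patients who stayed on drug. The documents do not support that. Without delays everyone has had the last dose by Day 140 to 165, so nobody is on drug in the tail. Nor does 6.7 distort the 12-month estimate: on the last-dose reading its earliest exit is Day 400. The one-dose case itself rests on reading an early stop as completion, which the text does not say. Exposure-linked censoring would bias the tail only if exposure predicts hazard among those still at risk, which has not been shown.

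Nor does disease assessment stop at month 12. Section 5.4 allows clinically indicated studies at other times, so later progression can be found, but detection then depends on clinical triggers.

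Finally, the size depends on the hazard shape, and 32% comes from one Hodgkin series. The trial also enrols ALCL and haploidentical patients, for whom sections 2.2 and 2.3 cite 3-year PFS of 64% (a peripheral T-cell lymphoma series) and 63%. These too lie beyond planned follow-up.

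**Conclusion.** The point holds for the secondary endpoints. Planned follow-up ends at about 16.6 to 18.1 months for six undelayed cycles, possibly 13 to 14 months after a single dose, and scheduled disease assessment ends at 12 months. Relapse, PFS and OS from this trial therefore cannot be set against the 2-year rates in section 2.1. On the assumed hazard shapes, doing so would credit an ineffective drug with 13 to 25 points of PFS at 12 months. The tail after month 12 rests on clinically indicated assessment and on follow-up that varies with treatment duration.

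The larger censoring risk lies in 6.2 to 6.5, because those exits can fall before month 12. Its size is unknown: 6.2 is not defined further, no exit rate is given, and the bounds above are illustrative.

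The calendar results assume no dose delays. Delays would lengthen follow-up, but would have to total about 6 to 7 months to reach 2 years.

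Criterion 6.7 does not limit the primary endpoint, which has its own window of 6 months from transplant (section 8.2). Exits under 6.2 to 6.5 could shorten that window for individual patients.

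**What to change.** 1. In section 6.0, separate going off treatment from going off study. Replace 6.7 with a fixed time from transplant for every treated patient, whatever the number of cycles or the reason for stopping, except withdrawal of consent. For example, use 24 months, with relapse and survival status after month 12 taken from routine clinic records. Progression dates after month 12 would still depend on when routine assessments were done, and the report should say so.
2. In section 8.5, report relapse, PFS and OS at 12 months and at that fixed time, state the censoring rule, and compare with historical rates only at the same time point.
3. If follow-up is not extended, keep patients who meet 6.2 to 6.5 in follow-up to 12 months, report only the 12-month estimates, and state that they are not compared with 2-to-4-year rates.

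No treatment rule changes and no procedure is added. Going to 24 months costs about 6 to 7 months more record-based follow-up for six-cycle patients, up to about 11 for a one-dose patient, in 20 patients, and a later final report. The 12-month fallback needs rewording, plus continued follow-up to month 12 for patients who would otherwise leave.
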